1.3.1 Clinical Experience in Relapsed Multiple Myeloma

A multicenter, open-label, randomized phase 2 study evaluated 2 doses of lenalidomide for relapsed, refractory multiple myeloma patients. Seventy patients were randomized to receive oral lenalidomide either 30 mg once-daily or 15 mg twice-daily for 21 days of every 28-day cycle. Patients with progressive or stable disease after 2 cycles received dexamethasone. Analysis showed an increased

grade 3/4 myelosuppression in patients receiving 15 mg twice daily as compared to those receiving 30mg daily (41% versus 13%, $P = .03$). Responses were evaluated according to European Group for Blood and Marrow Transplantation (EBMT) criteria. Overall response rate (complete, partial, or minor) to lenalidomide alone was 25% (24% for once daily and 29% for twice-daily lenalidomide). Median overall survival (OS) in the 30-mg once-daily and twice-daily groups was 28 and 27 months, respectively. Median progression free survival was 7.7 months on once-daily versus 3.9 months on twice-daily lenalidomide ($P = 0.2$). Dexamethasone was added in 68 patients and 29% responded. Time to first occurrence of clinically significant grade 3 / 4 myelosuppression was shorter in the twice daily group (1.8 vs 5.5 months, $P = .05$). Significant peripheral neuropathy and deep vein thrombosis each occurred in only 3%. Lenalidomide was active and well tolerated in relapsed, refractory myeloma, with the 30-mg once-daily regimen providing the basis for future studies as monotherapy and with dexamethasone³².

In a safety and efficacy study of single agent lenalidomide in relapsed and refractory multiple myeloma patients, lenalidomide 30 mg (days 1-21 of 28 day cycle) was given to 222 patients who had relapsed or progressed after 1 or more prior therapies³³. Sixty-seven percent of patients had had three or more prior therapies, and 45% had had one or more autologous stem cell transplants. Eighty and 43% of patients had had thalidomide and bortezomib based therapies respectively. The median dose of lenalidomide was 25 mg (5-30mg) and the median duration of treatment was 4.2 months (0.06-38). The overall response rate (complete and partial) was 26% with 2% complete response³³.

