Previous studies of lenalidomide alone in a similarly defined relapsed/refractory MM patient population has shown an overall response rate of 25%, which also included the addition of dexamethasone after 2 cycles to non-responding stable disease patients. We will consider this regimen promising if the true overall response rate is 50% or greater when lenalidomide is combined upfront with CT-011. Therefore, we will test the null hypothesis that the true overall response rate (ORR) is at most 25% (reflecting a combination regimen ORR that would not be of interest) versus our alternative hypothesis that the true ORR in patients treated with this combination regimen is at least 50%.

Decision Rule: The largest response rate where this treatment regimen would be considered ineffective in this population is 25%, and the smallest response rate that would warrant subsequent studies with this proposed regimen in this patient population is 50%. The following Three-Outcome phase II study design is a modification of the standard one-stage phase II design and uses a maximum of 29 evaluable patients to test the null hypothesis that the true response rate is at most 25%. Since we will include the 6 patients treated at the MTD from the phase I portion of the trial, this will require accruing an additional 23 evaluable patients for this phase of the study. Based on this study design, there are three possible outcomes:

- **Not promising**: This regimen will be classified as not promising with respect to the response rate in this patient population if at most 9 patients have any response after 4 cycles of therapy out of the total 29 evaluable patients.
- **Promising**: This regimen will be classified as promising with respect to increasing the response rate in this patient population if at least 12 patients have an observed response to treatment after 4 cycles of therapy out of the total 29 evaluable patients. Subsequent larger confirmatory studies may be warranted.

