The proportion of responses (partial and complete) will be calculated out of all eligible patients who receive any treatment in that disease group who are included in the phase II assessment. Assuming the number of responses is binomially distributed, 95% binomial confidence intervals will also be calculated for the estimate of the proportion of responses. All adverse events will be summarized by the NCI CTCAE v. 4 criteria, and tabulated across all patients who received any treatment with a focus on severe (grade 3+) adverse events and toxicities (i.e. those deemed at least possibly related to study treatment). In addition, we will summarize the proportion of patients who received dexamethasone after being stable disease but without response after 2 cycles of therapy. We will descriptively summarize how many of these patients were converted to response after the addition of dexamethasone. Since the addition of dexamethasone is part of the overall treatment regimen that is dependent on treatment outcome at a certain time point, we will not make other adjustments to the study design to evaluate these patients separately outside of this descriptive summarization of whether or not they received the dexamethasone. We will evaluate other clinical outcomes such as progression-free survival and overall survival using the methods of Kaplan-Meier, although these analyses will be exploratory and primarily to help describe the cohort itself.

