6.3 Clinical outcome definitions

Time to progression: TTP will be defined as the time from start of treatment until the date he or she has progression or dies. Any subject who has received study treatment but has neither progressed nor died will be censored on the date of his or her last tumor assessment. A subject who has not received study treatment and who has neither progressed nor died will be censored on the day he or she was enrolled.

Progression Free Survival: PFS will be defined as the time from study entry until disease progression or death at trial closure for the per protocol population. Patients who withdraw from the trial prior to disease progression and who are either lost to follow-up, die or who begin alternative treatments prior to progression, will have their data censored as of the date considered to be lost to follow-up, date of death, or the first day of alternative therapy.

Time to Response: A subject's time to response is defined as the time from first dose of study therapy until measurement criteria are first met for [VG]PR or CR or SD (whichever status is recorded first). Time to response is computed only for subjects whose best response is [VG]PR or CR.

Duration of Overall Response: The duration of overall response will be computed for subjects whose best response is either [VG]PR or CR or SD. It will be measured from the time measurement criteria are first met for complete response or partial response (whichever status is recorded first) until the first date of progressive disease or death. Subjects who neither progress nor die will be censored on the date of their last tumor assessment.

Overall Survival: A subject's survival time will be defined as the time from start of treatment to the date of his or her death. If the subject has not died, survival will be censored on last date the subject was known to be alive.

Response Rate: The tumor response rate will be defined as the total number of subjects whose best response is PR or VGPR or CR or SD, divided by the number of per protocol patients.

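### The decision rule in 6.1.2 counts response after 4 cycles, 6.3 counts best response with no time limit, and no rule scores a treated patient who responds and leaves before the cycle 4 evaluation

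*Combined protocol and SAP*

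**What the plan says.** **Decision rule (6.1.2).** The regimen is not promising "if at most 9 patients have any response after 4 cycles of therapy out of the total 29 evaluable patients", and promising "if at least 12 patients have an observed response to treatment after 4 cycles of therapy out of the total 29 evaluable patients". Ten or 11 responders is inconclusive. All three categories are tied to 4 cycles.

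**Analysis text (6.1.2).** "The proportion of responses (partial and complete) will be calculated out of all eligible patients who receive any treatment" and are included in the phase II assessment. A treated patient who leaves early therefore stays in the denominator and has to be given a value.

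**Outcome definition (6.3).** The response rate is "defined as the total number of subjects whose best response is PR or VGPR or CR" (the sentence goes on to add stable disease), over the per-protocol patients. No time limit is attached to best response.

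**Endpoint lists.** Section 2.1 makes response after 4 cycles the phase II primary endpoint and the rates after 8 and 12 cycles secondary. Section 2.3 and the synopsis put response after 4 cycles, and then at 8 and 12 months in responding patients, together under the primary endpoint.

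**Timing and confirmation.** The synopsis has response assessed at the end of every cycle. Sections 4.1 and 4.3 put the assessment at cycle 4, or earlier if needed. Appendix B, note a, requires two consecutive assessments for every response category.

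**The concern.** Several routes take a patient off treatment before the cycle 4 evaluation: progression, toxicity, patient decision, a delay of more than 4 weeks, or having to stop either drug (4.4, 5.1.5, 5.6, 5.7). A patient with a confirmed partial response who leaves in cycle 4 could be scored either way, depending on which section the analyst follows. Patients with stable disease at cycle 4 continue treatment, so a first response after cycle 4 is also possible. It would count under 6.3 and not under 6.1.2.

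Three responders separate not promising (9) from promising (12). In an open-label single-arm trial, leaving the window open means it could be settled after the responses are known.

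**Working it through.** **Inputs from 6.1.2:** n = 29; not promising at 9 or fewer; promising at 12 or more; null rate 0.25; target rate 0.50. X is the number of responders, taken as binomial(29, p).

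**Step 1. The plan's own figures.**

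| Quantity | Formula | Exact | Stated |
|---|---|---|---|
| Type I error | P(X ≥ 12), p = 0.25 | 0.039 | 4% |
| eta | P(X ≤ 9), p = 0.25 | 0.834 | 0.83 |
| pi | P(X ≥ 12), p = 0.50 | 0.868 | 0.87 |
| Type II error | P(X ≤ 9), p = 0.50 | 0.031 | 3% |

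All four reproduce. The design arithmetic is sound, and the question is only which patients make up X.

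**Step 2. One patient under each rule.**

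| Patient | 6.1.2 read as a cycle 4 landmark | 6.1.2 read as by cycle 4 | 6.3, best response |
|---|---|---|---|
| Confirmed PR, leaves before the cycle 4 evaluation | 0 | 1 | 1, if in the per-protocol set |
| First PR after cycle 4 | 0 | 0 | 1, if in the per-protocol set |

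**Step 3. Early losses (illustration).** Suppose the true best-response rate is 50% and a landmark reading loses 3 or 5 percentage points of it. The size of the loss is an assumption, because the documents give no figure for it.

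| Rate counted | pi = P(X ≥ 12) | False negative = P(X ≤ 9) |
|---|---|---|
| 0.50 | 0.868 | 0.031 |
| 0.50 − 0.03 = 0.47 | 0.785 | 0.061 |
| 0.50 − 0.05 = 0.45 | 0.717 | 0.091 |

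In patients, these losses average 0.03 × 29 = 0.87 and 0.05 × 29 = 1.45 responders.

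**Step 4. Late gains (illustration).** Suppose the rate at cycle 4 is 25% and an unlimited window adds 3 points, again an assumption. Then p = 0.28 and P(X ≥ 12) = 0.084, against 0.039.

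Steps 3 and 4 fix the true rate on different definitions. They are separate what-if cases, and their effects should not be added together.

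**The case against.** **The plan can be read consistently.** Section 6.1.2 never says that a responder who leaves early is a non-responder. Sections 4.1 and 4.3 allow earlier assessment, so a by-cycle-4 reading is available. Section 2.1 makes the 4-cycle rate primary, and 6.3 is a general definition that does not mention the cut-offs. This stands as far as it goes: the landmark reading is one of several. The patient might also be called non-evaluable, a term settled only for untreated patients (7.1). Section 5.7 says phase II withdrawals are not replaced, while 10.7 says some patients may be. More readings make a written rule more necessary.

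**The patient may not be a responder under 6.3 either.** A single PR without a second assessment may not qualify under Appendix B, and the per-protocol set is undefined. This is correct, and the fix has to deal with confirmation.

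**Stronger readings that the documents do not support.**

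- A reader might take the 4.2-month median treatment time in 1.3.1 and infer that 1 − 0.5^(112/(4.2 × 30.44)) = 45% of patients will be off treatment by the end of cycle 4. That median comes from a cited single-agent lenalidomide study, and the exponential curve is added. The figure covers all patients who stop, not responders who stop. With 26% responding in that study, everyone who stopped early could have been a non-responder.
- A reader might add late conversions on dexamethasone to the 25% null and infer a much larger false-positive rate. Section 6.1.2 says that its 25% already includes added dexamethasone, so on that statement the conversions would be counted twice. The 29% dexamethasone response in 1.3.1 comes from a study that added it for progressive or stable disease and whose overall response rate included minor responses. It is not a PR-or-better rate in stable patients.
- A reader might say that the stated error rates are valid for only one definition. They are binomial results for whichever endpoint the 25% and 50% describe. The plan does not say clearly which that is.

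**Conclusion.** The conflict is real and should be resolved before analysis. Two written definitions give the primary numerator different time windows, and no rule scores a treated patient who responds and leaves before the cycle 4 evaluation.

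The number of patients affected is not known and could be close to zero. What can be shown is sensitivity: under the assumed shifts of 3 to 5 points down or 3 points up, pi falls to 0.79-0.72, the false-negative rate rises to 6-9%, or the chance of wrongly calling the regimen promising about doubles to 0.084. These figures rest on the assumed shifts and on binomial counts with n = 29.

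The point concerns the time window alone. Counting stable disease as response in 6.3 is a separate and larger conflict, and correcting it would leave this one in place.

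**What to change.** Use one numerator for the 9 / 10-11 / 12 rule in both 6.1.2 and 6.3:

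1. A responder is a treated patient whose best IMWG response is PR or better at any assessment from first dose through the end-of-cycle-4 evaluation.
2. State how the two-consecutive-assessments requirement in Appendix B applies, in particular whether the confirming assessment of a response first seen at the end of cycle 4 may fall after that evaluation.
3. A treated patient who leaves earlier counts as a responder if this was met and as a non-responder otherwise.
4. Report best response at any time, and the rates after 8 and 12 cycles, as separate figures that do not feed the rule. Align 2.1, 2.3 and the synopsis with this.

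The cost is a few sentences. Serum M-protein is already measured every cycle, so most patients need no new data. The schedule of events plans 24-hour urine only as required for response assessment, and follow-up marrow in non-secretory disease only at the end of cycle 4 and at progression. The text should say how an early leaver without those results is scored.

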6.2 Safety Endpoints

We will describe the safety profile of treatment by the recording of adverse events experienced by patients in the trial and by the monitoring of clinical laboratory values. The safety analysis will be performed on the safety population, as defined below. Adverse events will be described using the NCI CTCAE V 4.0 criteria.

Laboratory assessments will also be described according to the NCI CTCAE criteria, with separate descriptions for grade 3 or 4 laboratory abnormalities. Clinically significant laboratory abnormalities will be described as well.

6.3 Clinical outcome definitions

Time to progression: TTP will be defined as the time from start of treatment until the date he or she has progression or dies. Any subject who has received study treatment but has neither progressed nor died will be censored on the date of his or her last tumor assessment. A subject who has not received study treatment and who has neither progressed nor died will be censored on the day he or she was enrolled.

Progression Free Survival: PFS will be defined as the time from study entry until disease progression or death at trial closure for the per protocol population. Patients who withdraw from the trial prior to disease progression and who are either lost to follow-up, die or who begin alternative treatments prior to progression, will have their data censored as of the date considered to be lost to follow-up, date of death, or the first day of alternative therapy.

Time to Response: A subject's time to response is defined as the time from first dose of study therapy until measurement criteria are first met for [VG]PR or CR or SD (whichever status is recorded first). Time to response is computed only for subjects whose best response is [VG]PR or CR.

Duration of Overall Response: The duration of overall response will be computed for subjects whose best response is either [VG]PR or CR or SD. It will be measured from the time measurement criteria are first met for complete response or partial response (whichever status is recorded first) until the first date of progressive disease or death. Subjects who neither progress nor die will be censored on the date of their last tumor assessment.

Overall Survival: A subject's survival time will be defined as the time from start of treatment to the date of his or her death. If the subject has not died, survival will be censored on last date the subject was known to be alive.

Response Rate: The tumor response rate will be defined as the total number of subjects whose best response is PR or VGPR or CR or SD, divided by the number of per protocol patients.

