5.8.3 Post-treatment Follow-up

After the end of study treatment (whatever the reason for discontinuation), the patient will be followed for 6 months. Adverse events will be followed for at least 30 days, during which time all procedures for the reporting of SAEs will be followed.

- a. All patients who discontinue the trial secondary to an adverse event thought to be related to protocol therapy (probably, possible, or definite) should be followed until resolution, stabilization, return to a baseline condition, or death. Overall and progression free survival will be determined through clinic visits or phone interviews with clinical research staff. Follow up data should be submitted at 1 month after protocol therapy discontinuation and then every 3 months until progression or death, whichever occurs first.

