Appendix B: IMWG Response Criteria

Serum and urine M-protein estimates will be performed every 4 weeks; except for assessment of CR, patients with measurable disease restricted to the SPEP (or UPEP) will need to be followed only by SPEP (or UPEP). Responses will be assessed according to the criteria of the International Myeloma Working Group⁶¹, and characterized as follows:

Response Category	Response Criteria ^a
SCR	CR as defined below plus 
 • Normal FLC ration and • Absence of clonal cells in bone marrow^b by immunohistochemistry or immunofluorescence^c
CR	Negative immunofixation on the serum and urine and disappearance of any soft tissue plasmacytomas and $\leq 5\%$ plasma cells in bone marrow ^b
VGPR	Serum and urine M-protein detectable by immunofixation but not on electrophoresis or 90% or greater reduction in serum M-protein plus urine M-protein level < 100 mg per 24 hours
PR	$\geq 50\%$ reduction of serum M-Protein and reduction in 24 hour urinary M-protein by $\geq 90\%$ or to < 200 mg per 24 hours If the serum and urine M-protein are unmeasurable ^d a $\geq 50\%$ decrease in the difference between involved and uninvolved FLC levels is required in place of the M-protein criteria If serum and urine M-protein are unmeasurable, and the serum free light assay is also unmeasurable, $\geq 50\%$ reduction in plasma cells is required in place of M-protein provided baseline bone marrow plasma cell percentage was $\geq 30\%$ In addition to the above, if present at baseline a $\geq 50\%$ reduction in the size of soft tissue plasmacytomas is also required
SD^e	Not meeting criteria for CR, VGPR, PR, or progressive disease
Relapse Category^f	Relapse Criteria
Progressive disease	Requires only one of the following: Increase of $\geq 25\%$ from baseline in: 
 • Serum M-component and/or (the absolute increase must be ≥ 0.5 g/dl)^g • Urine M-component and/or (the absolute increase must be ≥ 200 mg/24 hours) • In patients without measurable serum and urine M-protein levels the difference between involved and

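### PFS for patients who withdraw is censored at an undefined loss-to-follow-up date or at new therapy, not at the last disease assessment used for TTP, so unassessed time can count as progression-free

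*Combined protocol and SAP*

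**What the plan says.** Section 6.3 defines the endpoint: "PFS will be defined as the time from study entry until disease progression or death at trial closure for the per protocol population". The next sentence covers "Patients who withdraw from the trial prior to disease progression and who are either lost to follow-up, die or who begin alternative treatments" before progression, and says they "will have their data censored as of the date considered to be lost to follow-up, date of death, or the first day of alternative therapy". No section says how or when a patient comes to be regarded as lost.

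TTP, also in Section 6.3, has nominally the same events: "TTP will be defined as the time from start of treatment until the date he or she has progression or dies". Its censoring date differs. A treated subject who "has neither progressed nor died will be censored on the date of his or her last tumor assessment". Duration of response follows the TTP rule.

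On disease assessment:

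- Appendix B: "Serum and urine M-protein estimates will be performed every 4 weeks".
- Schedule of Events (5.8.6): serum and urine M-protein are marked up to end of treatment, and nothing is marked under Follow Up. Footnote i places the serum tests on day 3 of each cycle and off study.
- Section 4.4: monthly evaluations after the 30-day visit until progression, new therapy, death or study completion. Their content is not specified.
- Section 5.8.3 and footnote p: data at 1 month, then every 3 months. "Overall and progression free survival will be determined through clinic visits or phone interviews with clinical research staff".

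Section 6.1.2 calls the PFS analysis exploratory, but lists PFS among the factors that settle an inconclusive result (10 or 11 responders of 29).

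**The concern.** Most routes to progression in Appendix B need an M-protein, free light chain, marrow or imaging result. A phone call cannot supply one. If the PFS clock runs past the last such result, the patient is counted as at risk during a period in which progression could hardly be recorded.

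Take a patient with stable disease at a last M-protein in month 4 who is declared lost in month 10. TTP is censored at 4 months and PFS at 10, although both rest on the same progression event. The plan does not explain the difference.

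The trial has one arm, so no concurrent control shares the effect. What is at stake is the description of the cohort and, with 10 or 11 responders, one input to the call on whether the regimen is promising.

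**Working it through.** **The plan's own figures.** There is no PFS target, event count or power to reproduce. The response design reproduces with n = 29: P(X ≥ 12 | 0.25) = 0.039, P(X ≤ 9 | 0.50) = 0.031, eta = 0.834, pi = 0.868. These agree with the stated 4%, 3%, 0.83 and 0.87.

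**Direction.** Each Kaplan-Meier factor is 1 − d/n. Moving a censoring date later leaves every d unchanged and can only enlarge n. Each factor, and so the curve, stays equal or rises.

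**Size: inputs.** The true median is set at 7.7 months, the once-daily lenalidomide PFS in Section 1.3.1, used only for scale. Assumed, because the documents give no figure: a share w = 10–40% who withdraw before progression at a constant hazard unrelated to progression; a gap g of 1, 3 or 6 months from last assessment to censoring date, the same for everyone; no progression detected in the gap. One month corresponds to Section 4.4 and three months to Section 5.8.3. Six months is a further illustration.

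**Rate.** λ = ln 2 / 7.7 = 0.0900 per month. Events per patient are 1 − w, and person-months per patient are (1 − w)/λ + wg. The apparent rate is therefore λ / [1 + λg·w/(1 − w)]. For w = 20%, g = 3: 1 + 0.0900 × 3 × 0.25 = 1.0675, so the rate is understated by 1 − 1/1.0675 = 6.3%.

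**Kaplan-Meier median.** With h = λ/(1 − w), the share truly under observation is A(t) = exp(−ht). The share withdrawn but still in the risk set is G(t) = w(1 − exp(−ht)) for t < g, and w(exp(hg) − 1)exp(−ht) afterwards. The apparent curve is exp(−∫λA/(A + G)dt). Results (rate understated; median in months against a true 7.7):

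| Gap | w = 10% | 20% | 30% | 40% |
|---|---|---|---|---|
| 1 month | 1%; 7.8 | 2%; 7.9 | 4%; 8.0 | 6%; 8.2 |
| 3 months | 3%; 7.9 | 6%; 8.2 | 10%; 8.6 | 15%; 9.1 |
| 6 months | 6%; 8.1 | 12%; 8.6 | 19%; 9.3 | 27%; 10.5 |

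**With detection only at 4-weekly visits.** In a simulation with w = 20%, 6-month PFS is 0.608 uncensored and 0.608 when censored at the last assessment. Under the plan's rule it is 0.615, 0.625 and 0.634 for gaps of 1, 3 and 6 months. For w of 10–30% the median, which moves only in 4-week steps here, does not shift with a 1-month gap; otherwise it shifts by 0 to 1.8 months. The rise in 6-month PFS at w = 20% is 1.6, 4.6 and 7.1 points if the true median is 3.9 months (twice-daily, Section 1.3.1), and 0.4, 0.9 and 1.4 points if it is 11.1 months (TTP, Table 1-1).

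**Decision zone.** P(10 or 11 of 29) is 0.127, 0.235, 0.297, 0.275 and 0.102 at true response rates of 25, 30, 35, 40 and 50%.

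**Deaths.** The same sentence censors deaths after withdrawal. If a fraction f of PFS events are such deaths and hazards are constant, censoring them multiplies the median by 1/(1 − f): +5%, +11% and +25% for an assumed f of 5, 10 and 20%.

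**The case against.** A reader might infer that reported PFS will be materially too long. The documents do not support that.

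- Section 4.4 requires monthly evaluations until new therapy, and Section 5.7 follows removed patients on the study schedule where possible. If those evaluations include M-protein, the gap before new therapy is about one month and the effect is small.
- The Schedule of Events places M-protein at end of treatment, so a patient who starts other therapy soon afterwards has little or no gap. The date of loss is undefined and could be set at the last visit. It is therefore not established that both dates always fall after the last assessment.
- The largest figure, 10.5 months, needs 40% withdrawing, a 6-month gap for every one of them and no progression detected in it.
- With 29 patients, a 7.7-month median and 20% withdrawing, the estimated median ranges from about 4.3 to 13.0 months (central 95% of simulations). That is wide against a shift of 0.1–0.9 months.
- PFS is exploratory, has no threshold, and is weighed with toxicity and correlative outcomes.

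All of this limits the size and the consequence. It does not remove the inconsistency. Section 4.4 does not say what its evaluations contain, the schedule shows no M-protein in follow-up, Section 5.8.3 allows 3-monthly phone contact, and nothing bounds the gap before a patient is declared lost.

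**Conclusion.** The point holds as an inconsistent and partly undefined censoring rule whose error can run only one way. PFS is equal or higher than under last-assessment censoring, never lower.

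The size is conditional on the assumed withdrawal share and gap: from almost nothing (about 0.1–0.5 months on a 7.7-month median with a 1-month gap) to 0.2–1.4 months with 3 months and 0.4–2.8 months with 6 months. These are illustrations under constant hazards, not estimates for this trial.

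A reader might also infer that the trial's conclusion is compromised. It is not shown to be. PFS enters only when 10 or 11 patients respond, which has probability 0.10–0.30 over true response rates of 25–50%, and then as one factor among several.

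The censoring of deaths in the same sentence conflicts with an endpoint defined as progression or death. It is a separate fault and may be the larger one, but any sensible rewording of this sentence touches it.

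**What to change.** Replace the PFS censoring sentence in Section 6.3 with: *Patients without documented progression or death who withdraw, are lost to follow-up, or start alternative therapy are censored at their last adequate disease assessment before that event.* This matches the TTP and duration-of-response rules.

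Three things go with it:

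1. State openly that the new wording also stops the censoring of deaths, in line with the PFS definition, so that the change is not made silently.
2. Define adequate disease assessment (M-protein, free light chain, marrow or imaging) and when a patient is regarded as lost.
3. Reconcile the monthly evaluations of Section 4.4 with the 3-monthly clinic or phone follow-up of Section 5.8.3 and footnote p, and say whether they include M-protein.

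The censoring change needs no new data. The cost is a slightly shorter reported PFS, and a further shortening if any patients die after withdrawal without progression.
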